11.3 Follow-Up Phase

The follow-up period begins immediately post-procedure (once the subject exits the clinic).

PK cohort

Each subject will return for up to 6 follow-up visits (see **Section 5 Study Flow Diagram** and **Section 6 Schedule of Assessments**).

- Day 1 (24 hours \pm 3 hours after the baseline procedure)

- Day 3 (72 hours \pm 3 hours after the baseline procedure)
- Day 7 \pm 2 days
- Day 14 \pm 2 days
- Day 21 \pm 2 days
- Day 30 \pm 3 days

The protocol-required follow-up assessments through Day 30 will consist of:

- SNOT-22 questionnaire (at Days 14 and 30)
- Endoscopic examination, grading and video recording (at Days 7, 14, 21 and 30)
- Blood sample collection of 11 ml (at Days 1, 3, 7, 14, and 30)
 - All blood draws must occur in the morning and at approximately the same time of the day during the follow-up visits.

Randomized cohort

Each subject will return for up to 5 follow-up visits for endoscopic grading and video recording (see **Section 5 Study Flow Diagram** and **Section 6 Schedule of Assessments**).

- Day 7 \pm 2 days
- Day 14 \pm 2 days
- Day 21 \pm 2 days
- Day 30 \pm 2 days
- Day 60 \pm 7 days

Unscheduled visits

Subjects may come in for additional unscheduled office visits if necessary. Circumstances that may warrant additional visits include but are not limited to:

- Worsening of sinus symptoms, and/or
- Sinus-related adverse events requiring medical evaluation.

The assessment at an unscheduled visit will consist of:

- SNOT-22 questionnaire (PK cohort only), and,
- Endoscopic examination, grading and video recording.

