16.7 Sensitivity Analysis for the Primary Efficacy Endpoints

Since the primary efficacy endpoint in the randomized cohort is determined by an independent blinded sinus surgeon based on review of video-endoscopies taken at Day 30, interventions performed by clinical investigators prior to Day 30 can potentially confound the primary efficacy outcome. Therefore, a sensitivity analysis will be performed to test the robustness of the efficacy conclusion to actual interventions given. In this analysis, data imputations will be performed as follows:

- If prior to Day 30, a clinical investigator indicates on the Endoscopic Scoring Form that either frontal recess/FSO required oral steroids or surgical intervention, and such intervention was actually given, then the grades given by the independent reviewer will

be replaced by the grades given by the clinical investigator at the visit preceding such intervention.

- If oral steroids were actually prescribed for reasons other than either frontal recess/FSO, then the grades given by the independent reviewer will be replaced by the grades given by the clinical investigator at the visit preceding commencement of oral steroids (prior to Day 30).

Additional sensitivity analysis may be performed to assess the sensitivity of the primary efficacy conclusion to patterns of missing data. This will be detailed in the statistical analysis plan.

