8.4 Role of the Independent Reviewer

Video-endoscopies of the FSO at Day 14 and Day 30 from all subjects in the randomized cohort will be provided to an independent sinus surgeon reviewer for grading and determination of the primary and secondary efficacy endpoints. The reviewer will be independent from the study (i.e., not enrolling study subjects for the study) and masked to treatment assignment (i.e., not know which sides received the UP Drug-Coated Device and the UP Control Device). To reference the subjects' pre-dilation anatomy as needed, the independent reviewer will have access to the pre-procedure videos.

Video-endoscopies obtained pre-procedure, at Day 14 and at Day 30 will be labeled with subject ID and will be checked to ensure no subject-identifying information (e.g., images of subjects' face) is included before being provided to the independent reviewer.

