10.3.2.1 Sensitivity Analysis for Steroid and Surgical Interventions

Because the primary efficacy endpoint for the randomized cohort will be determined by the independent blinded sinus surgeon based on review of video-endoscopies taken at Day 30, interventions performed by clinical investigators prior to Day 30 can potentially confound this outcome. Therefore, a sensitivity analysis will be performed to test the robustness of the efficacy conclusion to actual interventions given. Use of clinically necessary high-dose corticosteroids (e.g., oral, parenteral, injection, budesonide or other sinus steroid irrigations/rinses or drops, nebulized steroids administered nasally) or surgical intervention (e.g., repeat balloon dilation or sinus surgery involving dissection of the FSO) during the study will be tabulated.

In this analysis, data imputations will be performed as follows:

- If at Day 7, 14 or Day 21, a clinical investigator indicates on the Endoscopic Scoring Form that the frontal recess/FSO required oral steroids or surgical intervention, and that intervention was actually given, then the grades given by the independent reviewer at Day 30 will be

replaced by the grades given by the clinical investigator at the visit preceding commencement of oral steroids.

- If oral steroids were actually prescribed for reasons other than frontal sinus obstruction, then the grades given by the independent reviewer at Day 30 will be replaced by the grades given by the clinical investigator at the visit preceding commencement of oral steroids.

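### The intervention sensitivity analysis changes the rater along with the time point, although masked grades from before the intervention are planned at Day 14 and obtainable from recorded video at other visits

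*SAP*

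**What the plan says.** The primary endpoint of the randomized cohort is the side-to-side difference in Day 30 patency grade, read from video by one independent, masked sinus surgeon (SAP 6.1 and 10.3.2).

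SAP 10.3.2.1 adds a sensitivity analysis for interventions before Day 30, with two triggers:

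- **First bullet.** At Day 7, 14 or 21 "a clinical investigator indicates on the Endoscopic Scoring Form that the frontal recess/FSO required oral steroids or surgical intervention", and the intervention was given.
- **Second bullet.** "If oral steroids were actually prescribed for reasons other than frontal sinus obstruction". The prescriber is not named.

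In both cases "the grades given by the independent reviewer at Day 30 will be replaced by the grades given by the clinical investigator" at the visit before oral steroids began. Protocol 16.7 has the same substitution. For interventions needed in the frontal recess or ostium, the reviewer's grades are to "be replaced by the grades given by the clinical investigator at the visit preceding such intervention"; for steroids given for other reasons, "the grades given by the independent reviewer will be replaced by the grades given by the clinical investigator at the visit preceding commencement" of the steroids.

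On what the masked reviewer receives, SAP 8.4 states: "Video-endoscopies of the FSO at Day 14 and Day 30 from all subjects in the randomized cohort will be provided to" the reviewer, who may also consult the pre-procedure videos.

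On what is recorded, protocol 11.3 states for the randomized cohort: "Each subject will return for up to 5 follow-up visits for endoscopic grading and video recording". Unscheduled visits also include "Endoscopic examination, grading and video recording". Protocol 17.4 counts these videos among the source documents that sites keep.

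On masking, protocol 17.3.2 gives the devices letter codes and has the first device discarded before the second is opened. It then lists who is blinded: research coordinators, sponsor representatives, monitors and the independent reviewer. Clinical investigators are not listed.

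**The concern.** A sensitivity analysis should change one thing, so that a changed result can be read. Here the question is whether interventions before Day 30 distorted the primary comparison. Going back to a visit before the intervention addresses it. Moving from the masked central reader to the site investigator does not, and it adds a second possible cause for any change.

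Under the first bullet the two are linked. The investigator who recorded that an ostium needed intervention is also the source of the grade that replaces the masked one. If that investigator tends to grade one side differently from the reviewer, the tendency enters the analysis in exactly the subjects where judgement was most engaged. It could make a robust result look fragile, or a fragile one look robust.

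**Working it through.** **1. What the substitution changes.** For an affected subject, let M30 be the reviewer's treatment-minus-control difference at Day 30. Let Mv be the reviewer's difference at the pre-intervention visit, and Iv the investigator's at that same visit. The plan replaces M30 with Iv, and

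Iv − M30 = (Mv − M30) + (Iv − Mv).

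The first term is the move back in time, which is the purpose of the analysis. The second is the change of rater, and the plan does not separate the two. Replacing M30 with Mv removes the second term.

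**2. Whether Mv is available.**

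| Last visit before intervention | Video recorded? | Masked grading planned? |
|---|---|---|
| Day 14 | Yes (protocol 11.3) | Yes, all randomized subjects (SAP 8.4, 6.2.2; protocol 17.3.2) |
| Day 7 or Day 21 | Yes (protocol 11.3) | No |
| Unscheduled | Yes (protocol 11.3) | No |
| Pre-procedure | Yes (protocol 11.2) | No; reviewer has access for reference (SAP 8.4) |

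At Day 14 the masked grade will already exist. Elsewhere one added reading by the same reviewer is needed.

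**3. The plan's own sample size.** Inputs from SAP 9.4.2: difference 0.5, SD 1.1, two-sided α = 0.05, power at least 90%. For the paired t-test with n = 53, the noncentrality is 0.5/1.1 × √53 = 3.309 and the critical value on 52 df is 2.007. Power is 0.901, and with n = 52 it is 0.895. The stated 53 is reproduced. The smallest observed difference that is significant at n = 53 is 2.007 × 1.1/√53 = 0.303 grade.

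**4. Illustrative size of the rater term.** If k of 53 subjects are replaced and the investigator's side difference departs systematically from the reviewer's by b grades, the mean shifts by (k/53) × b. Both k and b are assumptions. SD is held at 1.1.

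| k of 53 | b | Shift | Chance of significance, true difference 0.5, shift toward null | Chance of significance, true difference 0 |
|---|---|---|---|---|
| 3 | 0.25 | 0.014 | 0.88 | 0.05 |
| 5 | 0.5 | 0.047 | 0.84 | 0.06 |
| 11 | 0.5 | 0.104 | 0.73 | 0.10 |
| 11 | 1.0 | 0.208 | 0.48 | 0.27 |
| 16 | 1.0 | 0.302 | 0.25 | 0.50 |

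Without any rater term the two chances are 0.90 and 0.05.

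**5. Two gaps in the same wording.** The SAP's first bullet covers surgery but fixes the visit only by the start of oral steroids; protocol 16.7 refers to the visit before the intervention of either kind. The SAP also does not say whether one side or both are replaced. If only one is, that subject's difference sets an investigator's grade against the reviewer's.

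**The case against.** **Masking.** A reader might infer that investigators know the assignment and that the check is therefore unmasked. The documents do not support that. Devices are coded, side-by-side comparison is prevented, and SAP 9.1 gives blinding of study personnel as the reason for the codes. What stands is narrower: investigators handle each device, only one of which is coated, and the protocol's list of blinded personnel omits them.

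**Separability.** A reader might also infer that a rater effect could never be detected. That goes too far. SAP 10.4.2.1 and 10.4.2.2 report side-to-side patency by both raters, which allows comparison at Day 14 and Day 30. This is a partial check: it shows average disagreement over all subjects, not disagreement in those who had an intervention.

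**Scope of the trigger.** The argument that the grader is the person who judged the need fits the first bullet only. Under the second, steroids are given for other reasons. The change of rater applies to both.

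**Rationale for investigator grades.** Patency is defined by probing, which the investigator performs while the reviewer sees a video. But the primary endpoint is the reviewer's video grade, so a robustness check on it gains little from switching to the other measure.

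**Magnitude.** Disagreement without direction tends to average out, so only a systematic side-specific difference matters. The larger shifts in the table need both a high replacement share and a large b. The documents support neither figure.

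**Extra readings.** Videos sent outside the schedule, labelled by subject ID, could signal that a subject had an intervention. They would not reveal which side was treated. The reviewer's remit would widen, and some videos may not be gradable. The change has to provide for these points; they do not defeat it.

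**Conclusion.** The point holds as a weakness in one sensitivity analysis. For affected subjects SAP 10.3.2.1 and protocol 16.7 change rater and time point together, so a departure from the primary result cannot be cleanly attributed to interventions, and agreement with it is weaker support than a masked reading would give. Masked grades at the right time are either already planned or obtainable from recorded video.

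The primary analysis stays on the masked Day 30 grades, and nothing here suggests that the primary conclusion is compromised. The size cannot be derived from the documents. Over the assumed range of 3 to 16 of 53 subjects replaced and a rater difference of 0.25 to 1.0 grade, the shift runs from 0.01 to 0.30 grade against the planned 0.5. At the low end it is negligible. The change is worth making because it is cheap and gives the analysis a clear reading.

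**What to change.** Before database lock and unblinding, revise SAP 10.3.2.1, and either align protocol 16.7 or document the departure from it:

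1. For each affected subject, replace the Day 30 grades of **both sides** with the independent reviewer's grades from the last video before the intervention, whether steroid or surgical.
2. Where Day 14 is that visit, use the Day 14 masked grade already planned.
3. Otherwise have the same reviewer grade the existing video under the same masking, without being told why it was sent.
4. Use investigator grades only where that video cannot be graded. Label these cases and report their number.
5. Show the current investigator-grade version as a supplement.

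Item 1 also closes the two gaps on surgery and on sides. The rule still moves the time point, which is intended; it removes only the change of rater.

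The cost is wording plus a small number of readings by the same reviewer. If 15% of 70 subjects were affected (an assumption), that is 0.15 × 70 = 10.5, or about 10, and fewer where Day 14 applies. No new reader or study procedure is needed.

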6.2 Randomized Cohort

Assessment	Screening	Baseline/ Procedure	Day 7 (±2 d)	Day 14 (±2 d)	Day 21 (±2 d)	Day 30 (±2 d)	Day 60 (±7 d)
Informed consent	X						
Medical/surgical history	X						
CT scan (≤ 30 days prior to randomization)		X					
In-office bilateral FSO dilation		X					
Endoscopic grading and recording	X	X ^a	X	X	X	X	X
Video-endoscopy grading (independent reviewer)				X			X
Concomitant medications	X	X	X	X	X	X	X
Adverse events reporting	X	X	X	X	X	X	X
Urine pregnancy test (female subjects of childbearing potential)	X ^{b,c}	X ^{b,c}					
Documented birth control (female subjects)			X	X	X	X	X

Abbreviations: CT, computed tomography; d, day; FSO, frontal sinus ostium/ostia.

^a All endoscopic assessments performed prior to baseline procedure.

^b Female subjects with reproductive potential are required to undergo a urine pregnancy test at screening and prior to the baseline procedure.

^c Female subjects are required to confirm their nursing status at screening and baseline.

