10.2 Eligibility Criteria

Subjects are eligible for treatment (PK and randomized cohort) after they meet all of the following inclusion criteria and none of the following exclusion criteria.

Inclusion criteria

- a. Patient has provided written informed consent using a form approved by the reviewing institutional review board (IRB) and sponsor.
- b. Patient is ≥ 18 years of age.
- c. Patient is willing and able to comply with protocol requirements.
- d. Patient has a confirmed diagnosis of CRS, as defined in the 2016 “International Consensus Statement on Allergy and Rhinology”.
- e. Patient has bilateral disease in the frontal sinuses (Lund-Mackay score ≥ 1 on each side) on CT scan within 30 days prior to enrollment in the PK cohort and prior to randomization in the randomized cohort.
- f. Patient has had prior ESS (> 30 days with a healed mucosa), including bilateral ethmoidectomy (anterior or total) and uncinatectomy for better visualization of the FSO. Note: No additional surgical interventions will be allowed at baseline/procedure. Dilation of the maxillary and/or sphenoid sinus can be performed with a commercially available sinus dilation device, if clinically necessary, prior to randomization in the randomized cohort.
- g. Patient is able to tolerate topical/local anesthesia.
- h. Female patients of reproductive potential must not be pregnant or nursing and must agree to not become pregnant during their participation in the study.
- i. Female patients of childbearing potential must agree to use consistent and acceptable method(s) of birth control during their participation in the study.
- j. Patient has bilateral obstruction of the frontal recess/FSO due to scarring and/or polypoid edema confirmed on endoscopy (patency grade of 0 or 1 for each FSO).

k. Balloon dilation of the FSO with a 6 mm balloon is judged to be feasible (use light-assisted or image-guided instrument such as a frontal sinus seeker tip to confirm access of each FSO) and medically appropriate.

Exclusion criteria

- a. Patient has expanded amount of ethmoid polyposis (grade > 2 in the PK cohort, and grade \geq 2 in the randomized cohort).
- b. Complications from prior ESS or balloon dilation procedure (e.g., cerebrospinal fluid leak or injury to the skull base).
- c. History of aspirin exacerbated respiratory disease (AERD).
- d. Patient is a current smoker.
- e. Patient has known history of allergy or intolerance to MF.

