9.4.2 Randomized Cohort

The sample size was calculated based on the difference in the patency grade at Day 30 between the treatment and control sides with the following assumptions:

- Expected mean difference of 0.5 between the treatment and control sides in patency grade
- A SD of 1.1 for side-to-side difference in the patency grade of the FSO
- Target power of $\geq 90\%$
- Type I error rate of $\alpha = 0.05$, 2-sided

A mean difference in patency grade of 0.5 between the treatment and control sides favoring treatment sides was considered clinically meaningful. Based on standard formulas for a paired t-test, a sample size of 53 subjects provides at least 90% power to detect a difference of 0.5 in mean patency grade between treatment sides. Assuming up to 25% of subjects with non-evaluable data on one or both sides, additional 17 subjects will be enrolled for a total of 70 subjects in the randomized cohort.

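### For rescue that starts before the Day 7 visit, the sensitivity analysis can replace the Day 30 grade with a pre-dilation grade

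*SAP*

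**What the plan says.** The primary endpoint of the randomized cohort is the reviewer's Day 30 patency grade, compared between sides by a paired t-test. Because rescue before Day 30 may distort that grade, both documents plan a sensitivity analysis with two replacement rules.

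- **SAP 10.3.2.1.** If the investigator records at Day 7, 14 or 21 that the frontal sinus ostium needs oral steroids or surgery, and it is given, the reviewer's Day 30 grades are "replaced by the grades given by the clinical investigator at the visit preceding commencement of oral steroids". The second rule covers oral steroids prescribed for other reasons. It uses the same replacement and names no earliest visit.
- **Protocol 16.7.** Under the first rule, which covers any time before Day 30, the reviewer's grades will "be replaced by the grades given by the clinical investigator at the visit preceding such intervention".

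Four other provisions decide which grade that is:

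- The baseline footnote of the schedule (Protocol 6.2) reads "All endoscopic assessments performed prior to baseline procedure". SAP 8.2 likewise defines baseline as the last observation before the procedure.
- The first scheduled follow-up visit is Day 7 (Protocol 11.3, SAP 8.3).
- Inclusion criterion j (Protocol 10.2) requires "patency grade of 0 or 1 for each FSO".
- Unscheduled visits include endoscopic grading (Protocol 11.3). SAP 8.3 sends the handling of their data to Section 9.2, which does not mention them.

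**The concern.** A rule that steps back one visit works only if that visit came after dilation. In the first week no such scheduled visit exists, and neither document limits the replacement to post-dilation grades. The value carried forward can then predate both devices.

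The analysis is meant to show whether the efficacy conclusion is robust to the interventions given. A pre-device grade says nothing about that. A sinus that failed early on the drug side and one that failed early on the control side would be treated alike. The first error flatters the device and the second hides a benefit. Where the text allows two readings, two programmers could also assign different grades to the same subject.

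**Working it through.** **1. The plan's own figure.** SAP 9.4.2 gives "Expected mean difference of 0.5 between the treatment and control sides in patency grade" and "A SD of 1.1 for side-to-side difference in the patency grade of the FSO", with two-sided alpha 0.05 and at least 90% power. For a paired t-test the noncentrality is 0.5/1.1 × √53 = 3.31 on 52 degrees of freedom. Power is 0.901 with 53 pairs and 0.895 with 52, so the stated 53 is reproduced. This point does not affect it. The values 0.5 and 1.1 are reused below.

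**2. Which grade the rule selects.**

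| Situation | SAP 10.3.2.1 | Protocol 16.7 |
|---|---|---|
| Oral steroids start before the Day 7 visit, no graded unscheduled visit | Baseline, pre-dilation | Baseline, pre-dilation |
| Same, but a graded unscheduled visit came first | Use of that grade not defined | Use of that grade not stated |
| Oral steroids prescribed at the Day 7 visit and started after grading | Day 7 is a natural reading | Day 7 or baseline, depending on the reading |
| Surgical intervention done at the Day 7 visit | No anchor: the rule is dated by oral steroids | Baseline on one reading, Day 7 on another |

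**3. What a baseline replacement can show.** With 0 or 1 on each side, the pair difference can only be -1, 0 or +1, against -4 to +4 at Day 30. The grade is recorded before the randomization envelope is opened (Protocol 11.2 and 17.3.1), and sides are assigned 1:1, so its expectation is 0. This assumes that both sides are replaced. If only one side is, a 0 or 1 is set against a Day 30 reviewer grade, which biases the result against the replaced side.

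**4. Size when the early rescues are frontal failures.** The documents give no rate of early rescue. Assume 60 evaluable pairs, of which k were rescued early with a true pre-rescue post-dilation difference d, and the others average 0.5.

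Mean = [(60 − k) × 0.5 + k × d] / 60. Under the fallback the k pairs count 0 on average.

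| k | Fallback | d = -1 | d = -2 | d = -3 | d = +1 | d = +3 |
|---|---|---|---|---|---|---|
| 1 | 0.492 | 0.475 | 0.458 | 0.442 | 0.508 | 0.542 |
| 3 | 0.475 | 0.425 | 0.375 | 0.325 | 0.525 | 0.625 |
| 5 | 0.458 | 0.375 | 0.292 | 0.208 | 0.542 | 0.708 |

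For example, k = 5 and d = -3 gives (27.5 − 15)/60 = 0.208, against 27.5/60 = 0.458. The gap is k × |d| / 60: from 1/60 = 0.017 to 15/60 = 0.25.

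**5. Size when early rescue is unrelated to the frontal sinus.** Suppose a share f of subjects gets baseline grades on both sides and the rest keep mean 0.5 and SD 1.1. The mean is 0.5(1 − f). The variance is (1 − f) × 1.21 + f × v + f(1 − f) × 0.25, where v, the variance of the baseline difference, lies between 0 and 1. With 53 pairs, the power of this sensitivity analysis falls from 0.901 to 0.869–0.883 at f = 5% and to 0.832–0.862 at f = 10%. With 70 pairs and f = 10% it is 0.921–0.941, from 0.963.

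**The case against.** Several points on the other side have force.

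- **The Day 7 visit.** A reader might infer that every need flagged at Day 7 falls back on baseline, because Day 7 is a named trigger. The documents do not support that. Steroids prescribed at Day 7 normally start after that visit's grading, so Day 7 can itself be the preceding visit. Listing Days 7, 14 and 21 fits that reading equally well. What remains is the surgical case under one reading of Protocol 16.7.
- **The clearest case is not a frontal failure.** Oral steroids for another reason, under the second rule, reach baseline most plainly. Those subjects need not have a failing ostium, and exclusion h removes patients with oral-steroid-dependent asthma or COPD. For them the effect is dilution toward zero (step 5), not a lost failure.
- **Unscheduled visits.** A frontal failure in the first week would often lead to a graded unscheduled visit, which could supply a post-dilation value. This narrows the problem, but the SAP does not say whether such a grade counts.
- **Both sides.** The claim that the replaced pair carries no treatment effect needs both sides to be replaced. Neither document says so outright.
- **Scale.** A difference of 3 is about 2.7 times the planned SD of 1.1 (3/1.1), and step 4 puts all failures on one side. The -3 and +3 columns are extremes.
- **Scope.** Interventions are tabulated, and investigator-assessed patency and need for intervention are compared by side through Day 60 (SAP 10.4.2.2). Early failures therefore stay visible elsewhere.

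These points limit the reach of the concern. They do not remove the gap for interventions that start before Day 7 with no earlier post-dilation grade.

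**Conclusion.** The concern holds within limits. When an intervention starts before the Day 7 visit and no graded unscheduled visit came first, the stated rule substitutes a grade taken before either device was used. On one reading of Protocol 16.7 the same happens for a surgical intervention done at the Day 7 visit. If both sides are replaced, this sensitivity analysis cannot reflect early failure on either side.

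Under the assumptions of step 4, 1 to 5 early drug-side failures with differences of -1 to -3 should give means of 0.475 down to 0.208; the fallback reports 0.492 to 0.458. Control-side failures move the true mean the other way. The effect is small if early rescue is rare, and the number of early rescues is unknown.

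Two stronger conclusions might be drawn, and neither is supported. The primary result is not biased: the primary t-test, its alpha and the sample size do not use the rule. Nor does the rule always favor the device: the direction depends on which side failed. It is still worth correcting before database lock, because a stated rule gives a wrong value and wording alone repairs it.

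**What to change.** In SAP 10.3.2.1 and Protocol 16.7, define the replacement as follows:

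- Use the last post-dilation investigator grade recorded before the intervention, steroid or surgical, started. This includes a grade recorded at the visit where the need was noted and grades from unscheduled visits.
- Never use a pre-dilation grade.
- Take both sides from that same visit.
- If no post-dilation grade exists, set the pair to missing in this analysis and vary it over the 0–4 by 0–4 tipping-point grid, regardless of the 10% threshold in SAP 10.3.2.2.

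The last item is needed because a few pairs would not trigger the grid by themselves: 5 of 60 is 8.3%. They would simply be dropped, and in the step 4 example the mean becomes 0.50, more favorable to the device than the fallback's 0.458 when the failures are on the drug side. With 5 such pairs the grid spans (27.5 − 20)/60 = 0.125 to (27.5 + 20)/60 = 0.792.

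The cost is small. The grades are already collected and no visit or procedure changes. A few pairs become missing in this one sensitivity analysis, and a little more analysis work is needed.
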